2.10 Schedule of Events

[Table 1](#) below describes the schedule of events for all study visits.

Table 1. Schedule of Events for All Study Visits

Visit	Screening	Randomization /Baseline	Visit 1 TC	Visit 2	Visit 3	Visit 4	Visit 5	Early Term
Days	-7 ± 2 days	0	7(-5/+2)	28(-5/+2)	56(-5/+2)	84(-5/+2)	168 ± 5	
Informed Consent	X							
Medical History	X							
Demographics	X							
Inclusion/Exclusion Criteria	X							
Mini Mental State Exam	X							
4-Meter Walk Test	X							
Concomitant Medications	X	X	X	X	X	X	X	X
Physical Exam ¹	X			X		X	X	X
Vital Signs	X	X		X	X	X	X	X
ECG ²	X	X ²				X ²	X	X
Hematology/Chemistry/Urinalysis ^{12,13}	X ¹²	X		X	X ¹³	X	X ¹³	X
Lipid Profile		X		X		X	X	X
Coagulation		X		X		X	X	X
Thyroid Markers ³		X				X		X
Vitamin D		X				X		X
Bone Turnover Markers ⁴		X		X	X	X	X	X
Pituitary/Adrenal Hormone Blood Tests ⁵		X		X		X		X
PSA (males)	X					X		X
Pancreatic Endocrine Markers ⁶		X		X	X	X		X
DXA Scan		X				X	X	X
Physical Performance Assessments ⁷		X		X	X	X	X	X
Patient Reported Outcomes ⁸	X (pre-Fx. Only)	X		X	X	X	X	X
Plasma Concentration Blood Samples ⁹				X ⁹	X ⁹	X ⁹	X ⁹	
Diary Card ¹⁰		X		X	X	X		
IP Administration/Dispensation/Compliance ¹¹		X	X	X	X	X		X
Averse Events		X	X	X	X	X	X	X
Study Disposition							X	X

¹ Height and weight will be measured at Screening. Weight only at Visits 2, 4, and 5.

² At Randomization and at Visit 4, the ECG will occur at 2 hours post-dose.

³T3, T4, TSH

⁴ s-CTX and s-PINP

⁵ The hormones tested will include follicle stimulating hormone (FSH), luteinizing hormone (LH), sex-hormone binding globulin (SHBG), estradiol, cortisol, aldosterone, adrenocorticotrophic hormone (ACTH) and total and free testosterone.

⁶ Endocrine pancreatic markers include fasting insulin and fasting glucagon

⁷ 6MWT and BORG Scale, Grip Strength, and SPPB.

⁸ Pre-fracture PADLs/IADLs at Screening. SF-36 and post-fracture PADLs/IADLs at Randomization. Post-fracture PADLs/IADLs only at Visits 2 and 3. SF-36 and post-fracture PADLs/IADLs at Visits 4 and 5 and Early Termination.

⁹Samples will be drawn pre-dose and at 2 hours (± 10 min) post-dose at Visits 2, 3, and 4. Visit 5 sample may be drawn along with the other blood work samples.

¹⁰ Diary cards provided at Randomization and Visit 3, reviewed at Visits 2 and 4.

¹¹IP administration and dispensation at Randomization. Compliance only at Visit 1 TC. Compliance, administration, and dispensation at Visit 2. Compliance and dispensation at Visit 3. Compliance and administration at Visit 4. Compliance only at Early Termination.

¹²HbA1c test will be performed at Screening only.

¹³Visits 3 and 5 will only include testing for GGT, ALT, AST, and total bilirubin.

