2.4 Visit 1: Telephone Contact

Within 1 week of randomization, subjects will receive a telephone call to review concomitant medications, adverse events, and compliance. Subjects will be reminded to take their assigned study treatment at approximately the same time every morning, 30 minutes prior to breakfast.

2.5 Visit 2

Approximately 4 weeks (no more than 30 days) after randomization, subjects will report to the clinic following a minimum 10-hour fast at approximately 8 am (Visit 2). A pre-dose blood sample will be drawn for the fasting lipid profile. A pre-dose plasma concentration blood sample will be drawn, the subject will be provided with one dose of their assigned treatment, and a post-dose plasma concentration blood sample will be drawn at 2 hours (± 10 min). They will have a physical examination, including weight, and vital signs will be recorded. Subjects will provide safety assessment samples for hematology/chemistry/urinalysis plus additional blood samples for bone turnover markers, pituitary/adrenal hormones, coagulation, and pancreatic endocrine markers. Following these blood tests, subjects will be allowed to have a light snack. They will provide data for Grip Strength, and SPPB. Post-fracture PADLs/IADLs will be conducted by subject interview. Following the interviews, they will perform the 6MWT and BORG Scale.

Concomitant medications, adverse events, compliance, and the diary card will be reviewed. The next bottle of study treatment (30 capsules) will be dispensed. Subjects will be reminded to take their assigned study treatment at approximately the same time every morning, 30 minutes prior to breakfast. Subjects will be informed that they may have more doses than they will need and must return any extra study treatment at Visit 3.

2.6 Visit 3

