Approximately 8 weeks (no more than 60 days) after randomization, subjects will report to the clinic for Visit 3 and provide samples for plasma concentration, chemistry (GGT, ALT, AST, and total bilirubin), bone turnover markers and pancreatic endocrine markers. Vital signs will be measured. Subjects will provide data for Grip Strength, and SPPB. Post-fracture PADLs/IADLs will be conducted by subject interview. Following the interviews, they will perform the 6MWT and BORG Scale. Concomitant medications, adverse events, and compliance will be reviewed and the next bottle of study treatment (30 capsules) will be dispensed. Subjects will be informed that they may have more doses than they will need and must return any extra study treatment at Visit 4. They will receive a diary card to record their treatment administration and meal and snack times for 3 days prior to Visit 4. Subjects will be informed that they may have more doses than they will need and must return any extra study treatment at Visit 4. Visit 4 DXA scans should be scheduled at this time.

2.7 Visit 4

Approximately 12 weeks (no more than 90 days) after randomization, subjects will report to the clinic following a minimum 10-hour fast at approximately 8 am (Visit 4). A pre-dose blood sample will be drawn for the fasting lipid profile. A pre-dose plasma concentration blood sample will be drawn, the subject will be provided with one dose of their assigned treatment, and a post-dose plasma concentration blood sample will be drawn at 2 hours (± 10 min). Diary card data, concomitant medications, compliance, and adverse events will be reviewed. They will have a physical examination, including weight, and vital signs will be measured. They will provide safety assessment samples for hematology/chemistry/urinalysis and additional blood samples for bone turnover markers, serum calcium, vitamin D, thyroid markers, pituitary/adrenal hormones, PSA (males only), coagulation, and pancreatic endocrine markers. Following these blood tests, subjects will be allowed to have a light snack. Subjects will provide data for Grip Strength, and SPPB. Post-fracture PADLs/IADLs and SF-36 will be conducted by subject interview. Following the interviews, they will perform the 6MWT and BORG Scale. ECG and DXA scans will be performed. Visit 5 DXA scans should be scheduled at this time.

2.8 Visit 5

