6.12 Plasma Concentration Sample Collection

Blood samples to determine plasma study drug concentration will be collected at Visits 2, 3, 4 and 5 as shown in [Table 1](#).

Pre-dose samples will be collected on the appropriate days at 0 to 20 min pre-dose (Visits 2, 3, and 4). A single post-dose sample will be collected thereafter at 2 hours (\pm 10 min) post-dose (Visits 2, 3, and 4), plus one additional sample at Visit 5.

At each collection, 5 mL of blood will be collected into a Vacutainer tube containing lithium heparin (green top) and immediately placed in an ice bath. Within 30 minutes of collection, the plasma fraction will be separated by centrifugation at 2,500 rpm (1,000 x g) for 15 minutes at 4°C. The plasma fraction will be separated into equal aliquots and transferred into 2 labeled 5 mL polypropylene tubes and frozen at approximately -20°C or -70°C.

Blood volume collected for these samples will be approximately 20 mL total per subject.

Plasma concentration samples should be shipped on dry ice via overnight delivery to MicroConstants for analysis. Samples will ship only on a Monday, Tuesday or Wednesday to minimize the possibility of the samples being in transit over a weekend. Duplicate plasma concentration samples will ship after MicroConstants confirms receipt of the initial samples.

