7.5 Visit 2 (Day 28 -5/+2)

At Visit 2, the following will take place:

- Record concomitant medications

- Physical examination, including weight
- Vital signs (SBP, DBP, HR)
- Plasma concentration sample collection (pre-dose and 2 hours \pm 10 min post-dose)
- Hematology/Chemistry/Urinalysis
- Bone Turnover Markers
- Pituitary/Adrenal Hormone Blood Tests
- Pancreatic Endocrine Markers
- Fasting Lipid Profile
- Coagulation
- A Light snack is permitted after bloodwork has been completed.
- Grip Strength and SPPB (to be performed before the PADLs/IADLs)
- Post-fracture PADLs/IADLs
- 6MWT and BORG Scale (to be performed after the PADLs/IADLs)
- Record adverse events
- Review diary card
- Review study treatment compliance; administer and dispense/re-dispense study treatment

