7.6 Visit 3 (Day 56 -5/+2)

At Visit 3, the following will take place:

- Record concomitant medications
- Vital signs (SBP, DBP, HR)
- Plasma concentration sample collection (pre-dose and 2 hours \pm 10 min post-dose)
- GGT, ALT, AST, and total bilirubin
- Bone Turnover Markers
- Pancreatic Endocrine Markers
- Grip Strength and SPPB (to be performed before the PADLs/IADLs)
- Post-fracture PADLs/IADLs
- 6MWT and BORG Scale (to be performed after the PADLs/IADLs)
- Record adverse events
- Review study treatment compliance; dispense/re-dispense study treatment
- Provide diary card to record treatment administration and meal and snack times for 3 days prior to Visit 4
- Schedule the Visit 4 DXA scan.

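### Visit 3 requires paired pre-dose and 2-hour post-dose VK5211 samples and fasting markers, but the protocol schedules no clinic dose, fast or arrival time there

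*Protocol*

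**What the plan says.** **Sampling.** Protocol Table 1 footnote 9 calls for paired draws at Visits 2, 3 and 4. Section 6.12 sets the first window: "Pre-dose samples will be collected on the appropriate days at 0 to 20 min pre-dose (Visits 2, 3, and 4". It places the second draw 2 hours (±10 min) after the dose at the same visits. Section 7.6 lists the same pair for Visit 3.

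**Dosing at the visit.** Footnote 11 includes administration at Randomization, Visit 2 and Visit 4, but for Visit 3 it reads "Compliance and dispensation at Visit 3". Section 7.6 matches that: "Review study treatment compliance; dispense/re-dispense study treatment". The Visit 2 list in 7.5 has the extra word: "Review study treatment compliance; administer and dispense/re-dispense study treatment". In the narrative, 2.5 and 2.7 say that "the subject will be provided with one dose of their assigned treatment" between the two draws. Section 2.6 says only that "subjects will report to the clinic for Visit 3 and provide samples for plasma concentration", with other bloodwork, and mentions no dose.

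**Fasting and arrival.** Sections 2.5 and 2.7 state a 10-hour fast and arrival at about 8 am; 2.6 states neither. Pancreatic endocrine markers are nevertheless drawn at Visit 3 (2.6, 7.6), and footnote 6 defines them: "Endocrine pancreatic markers include fasting insulin and fasting glucagon".

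**Home dosing.** Subjects are told at Randomization, and reminded at Visits 1 and 2, to dose each morning half an hour before breakfast. The dosing diary covers the three days before Visits 2 and 4 (5.2, footnote 10).

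**Analysis.** SAP 2.10.2.2 summarises pre-dose and post-dose concentrations at Visits 2, 3 and 4, and the single value at Visit 5.

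**The concern.** The sampling rules presuppose a dose whose time the staff know. The visit rules for Visit 3 do not provide one. A subject who follows the written instructions can take the capsule at home, eat breakfast and then come to clinic. The pre-dose window has then already closed, the 2-hour draw depends on a dose time recalled by the subject, and insulin and glucagon are measured in the fed state. The sample may be skipped, or it may be drawn and filed as pre-dose. In the second case a post-dose concentration would be summarised as a trough. The SAP has no rule for Visit 3 values whose dose time is undocumented.

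**Working it through.** The three on-treatment clinic visits, side by side:

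| Item (source) | Visit 2 | Visit 3 | Visit 4 |
|---|---|---|---|
| Pre-dose and 2 h post-dose sample (footnote 9, 6.12, 7.5–7.7) | required | required | required |
| Clinic dose (footnote 11, 2.5–2.7, 7.5–7.7) | stated | not stated | stated |
| 10-hour fast (2.5–2.7) | stated | not stated | stated |
| Arrival about 8 am (2.5–2.7) | stated | not stated | stated |
| Snack allowed after bloodwork (7.5–7.7) | stated | not stated | stated |
| Fasting insulin and glucagon (Table 1, footnote 6) | drawn | drawn | drawn |
| Dosing diary for the preceding days (5.2, footnote 10) | yes | no | yes |
| Explicit instruction to hold the home dose | none | none | none |

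The Visit 3 omission is the same in the narrative, the footnote and the activity list.

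**Effect of a home dose on each draw.** Let the home dose be at time 0.
- Pre-dose draw: the window is −20 to 0 min. A subject who arrives after time 0 cannot meet it.
- Post-dose draw: the window is 120 − 10 = 110 min to 120 + 10 = 130 min. Meeting it requires knowing time 0. No clinic dose fixes it and no diary covers that day, so it would be the subject's report.

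Both draws therefore depend on the same uncontrolled time.

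**Share of PK samples.** On-treatment samples per subject: 3 visits × 2 = 6. Visit 3 contributes 2, and 2/6 = 33%. This is the share open to doubt under the written rules, not an estimate of the share actually affected.

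**PK blood volume.** Section 6.12 gives 5 mL per collection and says: "Blood volume collected for these samples will be approximately 20 mL total per subject".
- As scheduled: 2 (Visit 2) + 2 (Visit 3) + 2 (Visit 4) + 1 (Visit 5) = 7 draws; 7 × 5 = 35 mL.
- Without the Visit 3 pair: 5 draws; 5 × 5 = 25 mL.
- 20 mL corresponds to 20/5 = 4 draws.

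The stated figure does not reproduce from the schedule.

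**Where Visit 3 values go.**
- PK: the descriptive summary in SAP 2.10.2.2 and listing 16.2.6.02. The SAP table list names no separate table for that summary.
- Correlation with total lean mass (SAP 2.10.2.1, tables 14.2.05.1 and 14.2.05.2): this runs by visit and over all post-baseline visits combined. DXA is done only at Randomization, Visits 4 and 5, or early withdrawal (Protocol 6.10), and last observation carried forward is presented for Months 3 and 6 only (SAP 2.16). Visit 3 has no lean mass value, so its concentrations could enter only through pairing across visits, which no text specifies.

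**The case against.** The strongest reply is that a clinic dose at Visit 3 is implied. A draw up to 20 minutes before a dose and another 2 hours after it make sense only if staff control the dose. Table 1 marks the study-drug row at Visit 3, drug is on hand, and compliance is reviewed there, so a home dose could come to light. On this view one word is missing from a footnote and an activity list, and a site would infer the rest. The laboratory and pharmacokinetics manuals cited in 6.11, which are not available here, may also settle it. This stands as a reason not to assume that samples were lost. It does not remove the conflict, because a site reading footnote 11 and 7.6 literally gives no dose, and nothing in 2.6 tells subjects to come fasting.

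It is also fair that the protocol has no explicit instruction to hold the home dose at Visits 2 and 4. That gap is not peculiar to Visit 3. At Visits 2 and 4 the fast, early arrival and clinic dose largely imply the hold; at Visit 3 only the term pre-dose does.

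Two stronger inferences are tempting and are not supported:
- Protocol 9.4 names only Visits 2 and 4, which might suggest that the Visit 3 pair was meant to be dropped. But 9.4 also omits the scheduled Visit 5 sample, so it is an incomplete list.
- The 20 mL volume equals two pairs, which might suggest the same. But with Visit 5 kept, dropping Visit 3 gives 25 mL. The figure fits neither schedule and shows only that it is wrong.

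**Conclusion.** The contradiction is real and minor. Unless a site infers a held dose, both Visit 3 PK draws, 2 of 6 on-treatment samples per subject, have uncontrolled timing, and the Visit 3 insulin and glucagon may not be fasting values. The PK volume in 6.12 is wrong as written.

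A reader might go further and conclude that Visit 3 pre-dose samples are in fact missing or mislabelled, or that the secondary concentration–lean mass analysis is compromised. The documents do not support either. Site practice and the manuals are unseen, so no rate can be given, and Visit 3 has no DXA value to correlate with. The effect is confined to the Visit 3 part of a descriptive PK summary, its listing and the Visit 3 fasting markers. The primary endpoint, the 12-week randomised comparisons and the Visit 2 and 4 pairs are unaffected.

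The conclusion assumes that subjects follow the standing morning-dose instruction on the day of Visit 3 and that no manual overrides it.

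**What to change.** 1. In the protocol, add administration at Visit 3 to footnote 11, 2.6 and 7.6. State the same 10-hour fast, arrival at about 8 am and clinic dose as for Visits 2 and 4, with the home dose held and the dose time recorded.
2. In 6.12, change the PK volume from about 20 mL to about 35 mL. In the same edit, bring the visit list in 9.4 into line with the SAP.
3. In SAP 2.10.2.2, add one line for samples already collected: summarise Visit 3 values as pre-dose or post-dose only where source records document the dose time; otherwise list them only.

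SAP 2.14 reports that enrolment was stopped before 120 subjects were randomised, so item 1 helps only subjects with Visit 3 still ahead. Item 3 applies whatever the stage of the trial.

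The cost is a short protocol clarification and one SAP sentence. The downside is a Visit 3 about 2 hours longer, for the post-dose draw, or some Visit 3 PK values lost from the summary.

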3 STUDY OBJECTIVES

3.1 Primary Objective

The primary objective of this study is to determine the efficacy of VK5211 after 12 weeks of treatment by mean placebo-corrected percentage change in total body less head (TBLH) lean body mass assessed by whole body DXA scan.

3.2 Secondary Objective(s)

The secondary objectives of this study are:

- To assess the safety and tolerability of VK5211 after 12 weeks of treatment by comparing overall adverse events, vital signs, 12-lead ECG data, physical examinations, and hematology/chemistry/urinalysis data to placebo.
- To determine the efficacy of VK5211 after 12 weeks of treatment by mean placebo-corrected change in:
 - Hip bone mineral density (BMD) assessed by DXA
 - Total lean body mass
 - Appendicular lean body mass
 - Bone turnover markers (s-CTX and s-PINP)
- To assess plasma concentration of VK5211 near T_{max} and at trough levels in relation to total lean body mass.

The exploratory objectives of this study are to determine the efficacy of VK5211 compared to placebo after 12 weeks of treatment by:

- Physical Performance Assessments
 - 6MWT and BORG Scale
 - Grip Strength
 - SPPB
- Patient Reported Outcomes
 - Pre- and Post-fracture PADLs/IADLs
 - SF-36

4 STUDY SUBJECT SELECTION

4.1 Inclusion Criteria

Each subject must meet the following criteria to be eligible for the study (subjects may be re-screened for failure of inclusion/exclusion criteria after consultation with medical monitor):

1. Males or females ≥ 65 years old who experienced a hip fracture (occurring 3-11 weeks prior) with no residual surgical issues will be eligible for participation.
2. Subjects must be willing and able to sign informed consent.
3. Blood pressure within the following parameters: systolic blood pressure (SBP) < 180 mmHg and diastolic blood pressure (DBP) < 100 mmHg with a heart rate of 45 to 90 bpm measured at Screening after resting for 5 minutes in the seated position.
4. MMSE score ≥ 20 .
5. Ability to walk 4 meters at Screening with or without a cane or walker with a gait speed of ≤ 0.8 m/s.
6. Suitable for participation in the study in the opinion of the Investigator.

4.2 Exclusion Criteria

Subjects who meet any of the following criteria must be excluded from the study:

1. Clinically significant new illness in the 1 month prior to Screening. (The qualifying hip fracture does not count as a significant illness).
2. Cognitive impairment as indicated by a score of < 20 on the MMSE performed at Screening or as determined by Investigator judgment if 20 or higher.
3. Pathological fracture (e.g. fracture due to Paget's disease of bone, malignancy, etc.). Fracture due to postmenopausal osteoporosis is not considered pathological for this trial.
4. Glycosylated hemoglobin (HbA1c) $> 9.5\%$ at Screening.
5. Presence of hardware in the contralateral hip.
6. Previous participation in any clinical study with an investigational drug, biologic, or device within 4 weeks prior to Screening.
7. Previous participation in a VK5211 or LGD-4033 study.
8. Use of antibody-based therapy for bone disease within 6 months prior to Screening. Subjects taking antibody-based therapy may be weaned off and re-screened on a case-by-case basis pending evaluation by the Sponsor.
9. Use of the following medications within 30 days prior to Screening or during the study:
 - Hormone replacement therapy with estrogen agonists or SERMs (vaginal estrogens are permitted).
 - Teriparatide (Forteo) is excluded; [supplemental Vitamin D₃ and/or Calcium is permitted].
 - Initiation of ANY new bone active therapy after Screening for duration of the study and follow up period (examples include IV and oral bisphosphonates, Denosumab, Teriparatide, etc.)
10. History of severe allergies (i.e., anyone with a known history of anaphylaxis to medication[s] or allergens).

11. Subject who has donated any blood, or had significant blood loss not associated with the qualifying hip fracture within 56 days prior to dosing.
12. Subject who has donated plasma within 7 days prior to dosing.
13. History of regular smoking or tobacco use within 3 months prior to Screening.
14. Not suitable to participate in the study in the opinion of the Investigator including an existing physical or mental condition that may prevent compliance with the protocol.
15. Not suitable to participate in the study in the opinion of the Investigator on the basis of clinically significant laboratory values.
16. ECG will be performed at Screening. Subjects with QTcF interval >450 msec (or >500 msec in the presence of a bundle branch block or paced ventricular rhythm) or any other exclusionary cardiac conditions noted previously on the locally read ECG are excluded from study participation. Other abnormal findings on the ECG should be carefully considered and any subject excluded who, in the judgment of the PI, may not safely complete treatment in this study.
17. History of active or uncontrolled heart failure or hypertension within 3 months of Screening.
18. Symptoms of acute or unstable coronary artery disease within 6 months of Screening.
19. History of cerebrovascular disease within 1 year of Screening.
20. History of epilepsy or any other seizure disorder within 1 year of Screening.
21. History of unexplained or untreated syncope in the past 12 months.
22. History of organ transplantation.
23. Positive history of human immunodeficiency virus, or acute/active hepatitis B, or hepatitis C.
24. Malignancy within 5 years of Screening (with the exception of previously treated basal cell carcinoma and squamous cell skin carcinoma in-situ).
25. History (within 2 years prior to Screening) of alcohol or drug/solvent abuse.
26. Documented sensitivity to any of the ingredients in the Investigational Product (IP) formulation.

